3.2.3.3. Definition of Dose Limiting Toxicity

Toxicity will be graded according to National Cancer Institute Common Terminology Criteria for Adverse Events Version 5.0 (NCI CTCAE v5.0). A DLT is a toxicity observed in the first 28 days as defined below and considered possibly related to GS-1423.

A DLT may lead to permanent withdrawal of GS-1423 for the subject after discussion between the Investigator and Gilead.

Hematologic

- Grade 3 thrombocytopenia with clinically significant bleeding (ie, requires hospitalization, transfusion of blood products, or other urgent medical intervention)
- Grade ≥ 3 febrile neutropenia (absolute neutrophil count [ANC] $< 1.0 \times 10^9/L$ and fever $> 101^{\circ}\text{F}/38.3^{\circ}\text{C}$)
- Any Grade 4 hematologic laboratory abnormalities/AEs regardless of duration will be considered DLTs with the **exception** of

Grade 4 lymphopenia

Grade 4 neutropenia lasting ≤ 7 days that is not associated with fever (the use of growth factors is permitted)

Grade 4 anemia explained by underlying disease

Non-Hematologic

- Grade 4 non-hematologic (laboratory and non-laboratory) AEs will be considered DLT regardless of the duration
- Any \geq Grade 2 uveitis, blurred vision, eye pain, and/or reduction of visual acuity that does not respond to topical therapy and does not improve to Grade 1 severity within 2 weeks of the initiation of topical therapy OR requires systemic treatment will be considered as a DLT
- The following Grade 3 non-hematologic AEs **will be considered as DLTs**:

Any Grade 3 AE of unknown etiology consistent with an immune phenomenon that does not resolve to \leq Grade 1 or to baseline with immunosuppressive therapy within 3 weeks of its onset

Any Grade 3 central nervous system (CNS)-related AE of unknown etiology consistent with an immune phenomenon regardless of duration or reversibility

Alanine aminotransferase (ALT) or aspartate aminotransferase (AST) elevation $\geq 3 \times$ upper limit of normal (ULN), also showing elevation of serum total bilirubin of $> 2 \times$ ULN, without initial findings of cholestasis (elevated serum alkaline phosphatase)

- Any other non immune-related Grade 3 AE **except:**

Any Grade 3 endocrinopathy that is adequately controlled by hormonal replacement
Grade 3 AE of tumor flare (defined as local pain, irritation, or rash localized at sites of known or suspected tumor)

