5.5.6. Permanent Treatment Discontinuation

Study drug treatment must be discontinued for drug-related AEs described in [Table 5-10](#). Non-AE reasons for study treatment discontinuation can be found in Section [6.10.1](#).

Table 5-10. Drug-Related Adverse Events Requiring Discontinuation of GS-1423

| Toxicity Category* | Qualifying Severity/Duration |
|--------------------|--|
| Ophthalmic | 
• Grade 2 uveitis, blurred vision, eye pain, and/or reduction of visual acuity that does not respond to topical therapy and does not improve to Grade 1 severity within 2 weeks OR requires systemic treatment• Grade 3 or higher uveitis |
| Gastrointestinal | 
• Grade 3 or higher diarrhea, colitis |
| Neurologic | 
• Grade 3 or higher neurologic toxicities |
| Dermatologic | 
• Grade 3 or higher skin AE, suspected Stevens-Johnson syndrome, or toxic epidermal necrolysis |
| Pulmonary | 
• Grade 2 pneumonitis or interstitial lung disease that does not improve after 2 weeks or worsening despite dose delay and systemic corticosteroids (see Table 5-5)• Grade 3 or higher pneumonitis |
| Endocrinopathies | 
• Grade 3 endocrinopathies not adequately controlled with physiologic hormone replacement• Grade 4 or higher endocrinopathies |
| Hypersensitivity | 
• Grade 3 or higher bronchospasm, hypersensitivity reaction, or infusion-related reaction |

| Toxicity Category* | Qualifying Severity/Duration |
|--------------------|--|

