| Laboratory | 
Thrombocytopenia
 
• Grade 3 thrombocytopenia lasting > 7 days or associated with clinically significant bleeding (i.e. requires hospitalization, transfusion of blood products, or other urgent medical intervention)• Grade 4 thrombocytopenia 
Neutropenia
 
• Grade 4 neutropenia lasting > 7 days 
Electrolyte Abnormalities
 
• Grade 4 electrolyte abnormalities with clinical sequelae• Grade 4 electrolyte abnormalities unable to be corrected with supplementation/appropriate management within 72 hours of onset 
Liver Function Abnormalities (see Table 5-6)
 
• AST or ALT > 5 × ULN• Total bilirubin > 3 × ULN• Concurrent AST or ALT > 3 × ULN AND total bilirubin > 2 × ULN lasting > 7 days |
| Other | 
• Grade 2 or 3 adverse event (laboratory or non-laboratory) that does not resolve in ≤ 12 weeks• Recurrence of Grade 3 or higher adverse event (laboratory or non-laboratory)• Grade 4 non-hematologic adverse event |

* AE must be study drug related for discontinuation reasons to apply

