7.4. Gilead Reporting Requirements

Depending on relevant local legislation or regulations, including the applicable US Food and Drug Administration Code of Federal Regulations, the EU Clinical Trials Directive (2001/20/EC) and relevant updates, and other country-specific legislation or regulations, Gilead may be required to expedite to worldwide regulatory agencies reports of SAEs, serious adverse drug reactions, or suspected unexpected serious adverse reactions (SUSARs). In accordance with the EU Clinical Trials Directive (2001/20/EC), Gilead or a specified designee will notify worldwide regulatory agencies and the relevant IEC in concerned Member States of applicable SUSARs as outlined in current regulations.

Assessment of expectedness for SAEs will be determined by Gilead using reference safety information specified in the investigator's brochure or relevant local label as applicable.

All investigators will receive a safety letter notifying them of relevant SUSAR reports associated with any study drug. The investigator should notify the IRB or IEC of SUSAR reports as soon as is practical, where this is required by local regulatory agencies, and in accordance with the local institutional policy.

7.5. Clinical Laboratory Abnormalities and Other Abnormal Assessments as Adverse Events or Serious Adverse Events

Laboratory abnormalities without clinical significance are not recorded as AEs or SAEs. However, laboratory abnormalities (ie, clinical chemistry, hematology, and urinalysis) that require medical or surgical intervention or lead to study drug interruption, modification, or discontinuation must be recorded as an AE, as well as an SAE, if applicable. In addition, laboratory or other abnormal assessments (ie, ECG, x-rays, vital signs) that are associated with signs and/or symptoms must be recorded as an AE or SAE if they meet the definition of an AE or SAE as described in Sections 7.1.1 and 7.1.2. If the laboratory abnormality is part of a syndrome, record the syndrome or diagnosis (ie, anemia), not the laboratory result (ie, decreased hemoglobin).

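### Two entries in Protocol Table 5-10 conflict on stopping GS-1423 for a drug-related Grade 4 electrolyte abnormality that has no sequelae and is corrected within 72 hours

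*Protocol*

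**What the plan says.** Protocol Section 5.5.6 opens with "Study drug treatment must be discontinued for drug-related AEs described in" Table 5-10, and the table's footnote adds that "AE must be study drug related for discontinuation reasons to apply". Section 6.10.1 repeats that the AEs described there must lead to discontinuation.

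Two parts of the table cover Grade 4 electrolyte events:

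- **Laboratory row, electrolytes.** There are two triggers: "Grade 4 electrolyte abnormalities with clinical sequelae" and "Grade 4 electrolyte abnormalities unable to be corrected with supplementation/appropriate management within 72 hours of onset".
- **'Other' row, third bullet.** There is one trigger: "Grade 4 non-hematologic adverse event". It carries no condition. The bullet above it reads "Recurrence of Grade 3 or higher adverse event (laboratory or non-laboratory", so this row is not confined to clinical events.

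Section 7.5 says that laboratory abnormalities "that require medical or surgical intervention or lead to study drug interruption, modification, or discontinuation must be recorded as an AE".

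Section 3.2.3.3 deals with DLTs separately. Grade 4 non-hematologic "AEs will be considered DLT regardless of the duration", and laboratory events are expressly included.

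**The concern.** The electrolyte entries set conditions: a Grade 4 value is a reason to stop only if it has consequences or cannot be corrected in time. The 'Other' bullet sets none. An event that meets neither electrolyte condition can still meet the 'Other' bullet, and both entries sit in one table whose content is binding.

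What is at stake is how the subject is managed after a drug-related Grade 4 event. One investigator, reading the electrolyte entries, may treat the event as no reason to stop and move to the resumption rule in Section 5.5.5. Another, reading the 'Other' row, must withdraw the subject permanently. This is a first-in-human study (Section 1.2.3) with dose cohorts of 3 to 6 after the accelerated steps (Table 3-1). Different handling also feeds the SAP Section 7.1.6.1 summaries of TEAEs leading to premature discontinuation.

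**Working it through.** No sample size, power or error rate depends on this point, so the check applies the rules to one test case: a drug-related Grade 4 electrolyte abnormality, no clinical sequelae, corrected with supplementation in 48 hours.

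1. **Is it an AE?** Section 7.5 requires an abnormality needing medical intervention to be recorded as one. Taking supplementation as medical intervention, the answer is yes.
2. **Is the table binding for it?** Yes. It is drug-related, so Sections 5.5.6 and 6.10.1 both apply.
3. **Electrolyte entries.** There are no sequelae, and 48 hours is less than 72 hours. Neither trigger is met, so these entries do not require discontinuation.
4. **'Other' row.** The event is Grade 4, is not hematologic and is an AE. The trigger is met, so discontinuation is required.
5. **Does another section settle it?** Section 5.5.5 allows resumption once a drug-related AE resolves to Grade 1 or baseline. None of its exceptions concerns electrolytes. Section 5.5 lets the investigator withhold or stop a drug at any time, but it does not authorise continuing where the table says must. The SAP is silent.
6. **Is it a DLT?** Yes under Section 3.2.3.3, if it occurs in the first 28 days and is considered possibly related to GS-1423. The exceptions listed there cover Grade 4 hematologic and Grade 3 events, so none applies.
7. **Does the handling change the MTD count?** No. A subject with a DLT stays in the DLT set (Protocol Section 8.3.1.2, SAP Section 3.1.4), and only subjects who leave for reasons other than a DLT are replaced (Protocol Sections 3.2.3.1 and 4.1.1). After Day 28 the event does not enter the MTD rule at all.

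| Rule | Result for the test case |
|---|---|
| Table 5-10, electrolyte entries | Discontinuation not required |
| Table 5-10, 'Other' row | Discontinuation required |
| Section 3.2.3.3 | DLT if in the 28-day window and possibly related |

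The first two lines conflict. The third is a different question and has one answer.

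The only scale the documents offer is a ceiling. One subject is 1/3 = 33% to 1/6 = 17% of a cohort of 3 to 6. With at most 26 Q2W cycles (Section 3.4), withdrawal after the second dose forgoes at most 26 − 2 = 24 doses, assuming the subject would otherwise have completed a full year.

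**The case against.** The best defence is that Table 5-10 is a cumulative list of reasons to stop. Nothing in it grants permission to continue, so meeting any one trigger is enough. The 'Other' bullet then decides the case, and the electrolyte bullets are redundant but not contradictory. Other entries overlap in the same way: the Grade 4 endocrinopathy entry is largely covered by the 'Other' bullet too.

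Part of this stands. Continuation is only implied by the electrolyte entries. A reader might infer that the table expressly allows dosing to go on, and it does not. But the two overlaps differ. The endocrinopathy entry agrees with the 'Other' bullet, whereas the electrolyte entries carry two conditions that the cumulative reading would leave with no effect. The Grade 4 neutropenia entry, which also has a duration condition, keeps its force because the 'Other' bullet is limited to non-hematologic events. No matching exclusion was written for electrolytes.

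Two narrower readings of the 'Other' bullet would remove the conflict:

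- **Non-laboratory events only.** The bullet lacks the laboratory wording that its two neighbours carry. Against this, Section 3.2.3.3 uses the term non-hematologic to span laboratory and non-laboratory events.
- **A residual category**, with the specific electrolyte rule governing. Against this, the other two bullets in the row cut across all toxicity categories.

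Either reading is possible and neither is stated. A reader cannot claim that the text rules them out, but a site cannot rely on them either. Investigators are told in Section 5.5.1.2 to take questions on discontinuation to the medical monitor. That may limit divergence in practice, but it does not say which entry governs.

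**Conclusion.** The defect is real and lies wholly inside Table 5-10. For a drug-related Grade 4 electrolyte abnormality without sequelae, corrected within 72 hours, the two entries point to opposite actions, or else the electrolyte entries do nothing. The consequence is inconsistent subject management and re-exposure after such an event. No frequency is given, so the size is unknown beyond the ceiling above. The conclusion assumes that supplementation counts as medical intervention under Section 7.5.

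Two stronger conclusions are tempting and should not be drawn:

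- **That the DLT definition adds a third conflicting instruction.** Section 3.2.3.3 decides whether an event counts against a dose level. It says a DLT may lead to withdrawal after discussion, which fits either reading of Table 5-10. Its wording on duration already settles DLT status.
- **That the MTD is put at risk.** The count is the same whether or not the subject stays on drug. The RP2D rests on all available clinical data (Section 3.2.3.1), so any effect there is indirect.

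SAP Section 1 states that the study ended at completion of Part A and that later parts will not be initiated. This limits the prospective benefit of a correction. The ambiguity still applied to Part A subjects and to how their discontinuations are read.

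**What to change.** Reconcile the electrolyte entries and the 'Other' row of Table 5-10 so that this event gets one answer, and state the scope of the 'Other' row, including whether it reaches laboratory events that have their own entry. Which rule stands is for the sponsor's clinical team; this review takes no view. No change to the DLT definition is needed.

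The cost is a line or two in one table, with no new procedure, visit or data item.

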5.5.6.1. Treatment Compliance

Treatment delays from the protocol-specified treatment plan for greater than 4 weeks (QW or Q2W) or 6 weeks (Q3W) require consultation between the investigator and Gilead and written documentation of the collaborative decision on subject management.

Administration of study medications will be witnessed by the investigator and/or study staff. The total volume of study treatments infused will be compared with the total volume prepared to determine compliance with each dose administered.

Any reason for noncompliance should be documented. Drug treatment noncompliance is defined as a subject missing > 1 cycle of study treatment for non-medical reasons. If 1 cycle was missed and the interval between the subsequent treatment cycle and the last administered treatment cycle is longer than 4 weeks for non-medical reasons, criteria for insufficient compliance are met.

5.5.7. Treatment Beyond Initial Progressive Disease

Subjects who experience initial radiologic PD and are not doing well clinically will discontinue study drug treatment and no further imaging is required.

Subjects who experience initial radiologic PD and are doing well clinically are considered to have initial RECIST 1.1-defined PD and will be permitted, with Gilead's approval, to continue with study drug treatment. These subjects will be reevaluated using the same imaging modality no less than 4 weeks later to assess whether study drug treatment will be continued. To continue study drug treatment beyond initial RECIST 1.1-defined PD, they must meet the following criteria:

- There is investigator-assessed clinical benefit from the treatment
- Subject is clinically stable
- Subject is tolerating study drug and
- There is agreement with Gilead

The assessment of clinical benefit should take into account whether the subject is clinically deteriorating and unlikely to receive further benefit from continued treatment. The following criteria need to be taken into consideration:

- Absence of clinical symptoms and signs (including worsening of laboratory values) indicating PD,
- No decline in ECOG performance status attributed to underlying malignancy, and
- Absence of rapid progression of disease or of progressive tumor at critical anatomical sites (eg, spinal cord compression) requiring urgent alternative medical intervention.

5.5.7.1. Subsequent Anticancer Therapy

The investigator or qualified designee will review all new anticancer therapy initiated after the last dose of study treatment. If a subject initiates a new anticancer therapy within 30 days after the last dose of study treatment, the 30-Day Follow-up Visit must occur before the first dose of the new therapy. Once new anticancer therapy has been initiated, subjects will move into the first posttreatment visit at 3 months from last treatment dose, then survival follow-up thereafter.

5.6. Prior and Concomitant Medications

5.6.1. Acceptable Concomitant Medications

All treatments that the investigator considers necessary for a subject's welfare may be administered at the discretion of the investigator in keeping with the community standards of medical care. Concomitant medications, including all prescription, over-the-counter, herbal supplements, and IV medications and fluids received within 30 days before the first dose of study treatment through the 30-day follow-up visit should be recorded in the electronic case report form (eCRF). If changes occur during the study period, documentation of drug dosage, frequency, route, and date will also be included on the eCRF.

Palliative and supportive care is permitted during the course of the study for underlying medical conditions and management of symptoms.

Surgery for tumor control or symptom management is not permitted during the study. Palliative radiotherapy is permitted to a single lesion if considered medically necessary by the treating physician as long as the lesion is NOT a RECIST 1.1 defined target lesion and treatment is NOT administered for tumor control. Study therapy should be held during the course of palliative radiotherapy and should be resumed no earlier than the next scheduled administration of study therapy. The specifics of the radiation treatment, including the location, will be recorded.

5.6.1.1. Rescue Medications and Supportive Care

Subjects should receive appropriate supportive care measures as deemed necessary by the treating investigator including but not limited to the items outlined below.

For guidelines for continuing treatment with GS-1423, see Section [5.5.5](#).

- **Diarrhea:** Subjects should be carefully monitored for signs and symptoms of enterocolitis (such as diarrhea, abdominal pain, blood or mucus in stool, with or without fever) and of bowel perforation (such as peritoneal signs and ileus). In symptomatic subjects, infectious etiologies should be ruled out, and if symptoms are persistent and/or severe, endoscopic evaluation should be considered. All subjects who experience diarrhea should be advised to drink liberal quantities of clear fluids or rehydration solutions. If sufficient oral fluid intake is not feasible, fluid and electrolytes should be substituted via IV infusion.
- **Anemia:** Transfusions may be utilized as clinically indicated for the treatment of anemia but should be clearly noted as concurrent medications or in a transfusion page. Consider a potential immunologic etiology and follow the American Society of Clinical Oncology (ASCO) guidelines for use of erythropoietin or derivatives.
- **Neutropenia:** Prophylactic use of colony-stimulating factors including granulocyte colony-stimulating factor (G-CSF), PEGylated G-CSF, or granulocyte macrophage colony-stimulating factor is not allowed in this study. Therapeutic use of G-CSF is allowed in subjects with Grade 3 to 4 febrile neutropenia. Consider a potential immunologic etiology.

- Thrombocytopenia: Transfusion of platelets may be used if clinically indicated. Immune thrombocytopenia purpura should be ruled out before initiation of platelet transfusion.
- Anti-infectives: Subjects with suspected or documented infectious complication should receive oral or IV antibiotics or other anti-infective agents as considered appropriate by the treating investigator for a given infectious condition, according to standard institutional practice.
- Adverse events with a potential immunologic etiology (irAEs): Follow ASCO or local institutional practice guidelines for identification, evaluation, and management of adverse experiences of a potential immunologic etiology. Depending on the type and severity of an irAE, oral or IV treatment with a corticosteroid should be considered, in addition to appropriate symptomatic treatment of a given condition (see Section [5.5.4](#) for management algorithms guidance).

5.6.2. Prohibited and/or Restricted Treatments

Subjects are prohibited from receiving the following therapies and treatments during the study. Study treatment will be discontinued in subjects who, in the assessment by the investigator, require the use of any of the following therapies and treatments for clinical management:

- Immunotherapy not specified in this protocol
- Chemotherapy
- Investigational agents other than GS-1423
- Corticosteroids are not permitted with the following exceptions:

As premedication for known hypersensitivity reactions (e.g. IV contrast, IV drug infusion);

Note: Premedication should not be administered routinely prior to dosing of GS-1423. Refer to Section [5.5.3](#) for subsequent premedication recommendations following GS-1423-related infusion reactions. Premedication for mFOLFOX6 should follow local SmPC or institutional guidance.

Intraocular, intranasal, inhaled, and/or topical corticosteroids; and/or

Prednisone at doses of up to 10 mg per day or equivalent.

- Live vaccines within 30 days prior to first dose of study therapy and while participating in study

There are no prohibited therapies during the Posttreatment Follow-up Phase.

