5.5.4.5. Endocrine irAEs

Rule out non-inflammatory causes. If a non-inflammatory cause is identified, treat accordingly and continue therapy per protocol. Consider visual field testing, endocrinology consultation, and imaging.

Table 5-7. Endocrine irAE Management Algorithm

| Endocrine irAEs | | |
|---|---|---|
| Endocrine Disorder | Management | Follow-up |
| Asymptomatic TSH abnormality. | Continue GS-1423 therapy per protocol. If $TSH < 0.5 \times \text{lower limit of normal (LLN)}$ or $TSH > 2 \times \text{ULN}$, or consistently out of range in 2 subsequent measurements: Include free thyroxine at subsequent cycles as clinically indicated; consider endocrinology consult. | |
| Symptomatic endocrinopathy. | Evaluate endocrine function. Consider pituitary scan. Symptomatic with abnormal lab/pituitary scan: Delay GS-1423 therapy per protocol; 1-2 mg/kg/day methylprednisolone IV or oral equivalent; initiate appropriate hormone therapy. No abnormal lab/pituitary MRI scan but symptoms persist: Repeat labs in 1-3 weeks, MRI in 1 month. | If improves (with or without hormone replacement): Taper corticosteroids over ≥ 1 month and consider prophylactic antibiotics for opportunistic infections. Resume GS-1423 therapy per protocol. Subjects with adrenal insufficiency may need to continue corticosteroids with mineralocorticoid component. |
| Suspicion of adrenal crisis (eg, severe dehydration, hypotension, shock out of proportion to current illness) | Delay or discontinue GS-1423 therapy per protocol. Rule out sepsis. Stress dose of IV corticosteroids with mineralocorticoid activity. IV fluids. Consult endocrinologist. If adrenal crisis ruled out, treat as above for symptomatic endocrinopathy. | |

irAE immune related adverse event; IV intravenous; LLN lower limit of normal; MRI magnetic resonance imaging; TSH thyroid stimulating hormone; ULN upper limit of normal.

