5.5.4.6. Renal irAEs

Rule out non-inflammatory causes. If a non-inflammatory cause is identified, treat accordingly and continue therapy per protocol.

Table 5-8. Renal irAE Management Algorithm

| Renal irAEs | | |
|---|--|--|
| CTCAE Grade of Creatinine Elevation | Management | Follow-up |
| Grade 1 Creatinine > ULN and > baseline but $\leq 1.5 \times$ baseline. | Continue GS-1423 therapy per protocol. Monitor creatinine weekly. | If returns to baseline: Resume routine creatinine monitoring per protocol. If worsens: Treat as Grade 2 or Grade 3-4. |
| Grade 2-3 Creatinine $> 1.5 \times$ baseline to $\leq 6 \times$ ULN. | Delay GS-1423 therapy per protocol. Monitor creatinine every 2-3 days. 0.5-1.0 mg/kg/day methylprednisolone IV or oral equivalent. Consider renal biopsy. | If returns to Grade 1: Taper corticosteroids over ≥ 1 month, consider prophylactic antibiotics for opportunistic infections, and resume GS-1423 therapy and routine creatinine monitoring per protocol. If elevations persist > 7 days or worsen: Treat as Grade 4. |
| Grade 4 Creatinine $> 6 \times$ ULN | Discontinue GS-1423 therapy per protocol. Monitor creatinine daily. 1.0-2.0 mg/kg/day methylprednisolone IV or oral equivalent. Consult nephrologist. Consider renal biopsy. | If returns to Grade 1: Taper corticosteroids over ≥ 1 month and add prophylactic antibiotics for opportunistic infections. |

CTCAE Common Terminology Criteria for Adverse Events; irAE immune related adverse event; IV intravenous; ULN upper limit of normal.

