5.5.4.7. Neurological irAEs

Rule out non-inflammatory causes. If a non-inflammatory cause is identified, treat accordingly and continue therapy per protocol.

Table 5-9. Neurological irAE Management Algorithm

| Neurological irAEs | | |
|--|---|--|
| CTCAE Grade of Neurological Toxicity | Management | Follow-up |
| Grade 1 Asymptomatic or mild symptoms; intervention not indicated. | Continue GS-1423 therapy per protocol | Continue to monitor subject. If worsens: Treat as Grade 2 or Grade 3-4. |
| Grade 2 Moderate symptoms; limiting instrumental ADL. | Delay GS-1423 therapy per protocol. Treat symptoms per local guidelines. Consider 0.5-1.0 mg/kg/day methylprednisolone IV or oral equivalent. | If returns to baseline: Resume GS-1423 therapy per protocol. If worsens: Treat as Grade 3-4. |
| Grade 3-4 Severe symptoms; limiting self-care ADL; life-threatening. | Discontinue GS-1423 therapy per protocol. Obtain neurology consult. Treat symptoms per local guidelines. 1.0-2.0 mg/kg/day methylprednisolone IV or oral equivalent. Add prophylactic antibiotics for opportunistic infections. | If improves to Grade 2: Taper corticosteroids over \geq 1 month. If worsens or atypical presentation: Consider IV immunoglobulin or other immunosuppressive therapies per local guidelines. |

ADL activities of daily living; CTCAE Common Terminology Criteria for Adverse Events; irAE immune related adverse event; IV intravenous.

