5.5.5. Criteria to Resume Treatment

Subjects may resume treatment with GS-1423 when drug-related AE(s) resolve(s) to Grade 1 or baseline value, with the following exceptions:

- Subjects may resume treatment in the presence of Grade 2 fatigue.

- Subjects with combined Grade 2 AST/ALT **and** total bilirubin values lasting > 7 days meeting discontinuation parameters (Section 5.5.6) should have treatment permanently discontinued.
- Drug-related Grade 2 pulmonary toxicity or colitis must have resolved to baseline before treatment is resumed.
- Drug-related endocrinopathies adequately controlled with only physiologic hormone replacement may resume treatment. (Exception: Study treatment does not need to be delayed/interrupted for subjects who experience immune-related hypothyroidism [Grades 1-2].)
- Subjects who received systemic corticosteroids for management of any drug-related toxicity must be off corticosteroids or have tapered down to an equivalent dose of prednisone \leq 10 mg/day.

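### Section 5.6.2 ends treatment for the systemic steroids that the protocol's own irAE rules use before restarting GS-1423: wrong as written, small in effect

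*Protocol*

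**What the plan says.** Section 5.6.2 of the protocol gives a list of prohibited therapies and the consequence of needing one: "Study treatment will be discontinued in subjects who, in the assessment by the investigator, require the use of any of the following therapies". Corticosteroids are on the list: "Corticosteroids are not permitted with the following exceptions". Three exceptions follow: premedication for known hypersensitivity; intraocular, intranasal, inhaled or topical use; and prednisone up to 10 mg/day or equivalent.

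Other sections treat systemic steroids as part of managing a toxicity from which the subject may return to GS-1423:

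- Section 5.6.1.1, on irAEs: "oral or IV treatment with a corticosteroid should be considered". The same section sends the investigator to Section 5.5.5 on continuing treatment: "For guidelines for continuing treatment with GS-1423, see Section" 5.5.5.
- Section 5.5.5: "Subjects who received systemic corticosteroids for management of any drug-related toxicity must be off corticosteroids or have tapered down" to 10 mg/day prednisone equivalent or less before GS-1423 is resumed.
- Section 5.5.4, Table 5-8, Grade 2-3 creatinine elevation: "0.5-1.0 mg/kg/day methylprednisolone IV or oral equivalent", with GS-1423 delayed and then resumed.
- Section 5.5.4, Table 5-7, symptomatic endocrinopathy with an abnormal laboratory result or scan: "1-2 mg/kg/day methylprednisolone IV or oral equivalent; initiate appropriate hormone therapy", again with delay and resumption.
- Section 5.5.4, Table 5-9, Grade 2 neurological toxicity: steroid to be considered, then "If returns to baseline: Resume GS-1423 therapy per protocol".

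Section 6.10.1 adds three relevant reasons to stop treatment: use of a drug barred by Section 5.6.2 (the sponsor may be consulted); a need for more than 10 mg/day prednisone equivalent lasting over 6 weeks; and a delay leaving the subject undosed for over 4 weeks on QW or Q2W, or over 6 weeks on Q3W.

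**The concern.** An investigator treating a resumable irAE with systemic steroid finds two instructions. Section 5.6.2 ends GS-1423 because the steroid was needed. Sections 5.5.4 and 5.5.5 hold GS-1423 and restart it once the event and the steroid dose have come down. Two sites could each follow the protocol and handle the same event differently.

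The stake is how the event is counted and how long the subject stays on drug. SAP Section 7.1.6.1 tabulates TEAEs leading to premature discontinuation separately from TEAEs leading to temporary interruption, and SAP Section 4.1 summarises reasons for discontinuing study drug by dose cohort. The rule that was followed decides which table the event enters.

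**Working it through.** There is no plan figure to reproduce; this is a comparison of text with a short dose calculation.

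**Step 1. Resumable rows with systemic methylprednisolone (Section 5.5.4).**

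| Table | Row | Dose, mg/kg/day | Minimum taper |
|---|---|---|---|
| 5-3 | Rash, Grade 1-2, persistent or recurrent | consider 0.5-1 | 1 month |
| 5-4 | Diarrhea/colitis, Grade 2, persistent or recurrent | 0.5-1 | 1 month |
| 5-5 | Pneumonitis, Grade 2 | 1 | 1 month, restart after the taper |
| 5-6 | Liver tests, Grade 2, persistent or worsening | 0.5-1 | 1 month |
| 5-7 | Symptomatic endocrinopathy, abnormal lab or scan | 1-2 | 1 month |
| 5-8 | Creatinine, Grade 2-3 | 0.5-1 | 1 month |
| 5-9 | Neurological, Grade 2 | consider 0.5-1 | none stated |

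Five of the seven direct the steroid (two of them only if the event persists, recurs or worsens) and two say to consider it. Rows that already stop GS-1423 are left out, because there the sections agree on the outcome.

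**Step 2. Do these doses breach the 10 mg/day limit?** Daily dose = mg/kg/day x body weight. At 70 kg (the standard weight used in Section 1.5):

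- 0.5 x 70 = 35 mg/day; 35/10 = 3.5 times the limit
- 1 x 70 = 70 mg/day; 7 times
- 2 x 70 = 140 mg/day; 14 times

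The lowest dose equals the limit at 10/0.5 = 20 kg, so in practice any adult exceeds it. This assumes methylprednisolone is at least as potent as prednisone, mg for mg. If more potent, the excess is larger.

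**Step 3. Do the exceptions cover the use?** Treating an irAE is not premedication, not local or inhaled use, and not at or below 10 mg/day. Section 5.6.2 refers to Section 5.5.3 for premedication after infusion reactions, but not to Section 5.5.4 or 5.5.5. No other section adds an exception.

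**Step 4. The 6-week bullet in Section 6.10.1.** If a need for more than 10 mg/day already ends treatment, a rule that ends it after 6 weeks above 10 mg/day has almost nothing left to do.

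**Step 5. How much does the dosing-gap rule absorb?** Part A, the only part run (SAP Section 1), was dosed Q2W, so the limit is 4 weeks. Six of the seven rows set a taper of at least a month. Section 5.5.5 allows restart at 10 mg/day, before the taper ends, except that Table 5-5 restarts only afterwards. As a rough check, assume a straight-line taper to zero over 30 days and methylprednisolone at 1.0 to 1.25 times prednisone; neither is in the documents. Days to reach 10 mg/day from dose D are 30 x (1 - 10/D). From 0.5 mg/kg (D = 35 to 44 mg) this is about 21 to 23 days; from 2 mg/kg (D = 140 to 175 mg), about 28 days. Days at full dose and the time from last infusion to steroid start come on top. So the 4-week rule would end treatment in many of these cases whichever section governs. The row least affected is Table 5-9, Grade 2, which sets no minimum taper.

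**The case against.** The best defence is that the intent is plain. Section 5.6.2 cannot be read with full literalness: the same list bars chemotherapy without exempting mFOLFOX6, which Section 5.4.2 gives to Phase 1b Cohort 1 and whose premedication a note in Section 5.6.2 itself covers. Section 5.5.2 says to delay until the resumption criteria are met. Table 5-10 stops GS-1423 for Grade 2 pneumonitis when it fails to improve or worsens despite delay and steroids, so steroid use alone is not the trigger there. Section 5.5.1.2 directs questions on interruption or discontinuation to the medical monitor, and Section 6.10.1 allows sponsor contact about a barred drug. Table 5-9 says only to consider steroid, whereas Section 5.6.2 applies when the investigator judges it required. The SAP also lists discontinuation reasons (4.1), reasons for delayed or missed doses (4.2.1) and concomitant medications (7.4.2), so a reader could largely reconstruct what happened.

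Much of this stands. It makes different handling between sites unlikely to be common. It does not remove the conflict: no text says which section prevails, and sponsor contact on a barred drug is optional.

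Three stronger readings are tempting and not supported:

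- That Section 6.10.1 directly contradicts Section 5.6.2 by permitting 6 weeks of steroid. Its bullets are independent sufficient reasons to stop; the 6-week bullet becomes redundant, not contradicted.
- That many subjects could still resume, because Section 5.5.6.1 counts delay from the treatment plan. That section requires consultation; it does not replace the stopping rule in Section 6.10.1.
- That irAE steroids would be recorded as protocol deviations. Section 7.7.2.2 speaks of inappropriate use of prohibited drugs, which need not include treatment given under Section 5.5.4.

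**Conclusion.** Section 5.6.2 is wrong as written: followed literally, it stops GS-1423 in subjects whom Sections 5.5.4 and 5.5.5 hold and restart. The dose comparison does not depend on fine assumptions, since the lowest dose is 3.5 times the limit at 70 kg.

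The effect is small. The irAE rules were evidently meant to govern, and the 4-week dosing gap (6 weeks on Q3W) ends treatment in many of the same cases. What remains is mainly resumable events with short steroid courses, with Grade 2 neurological events the clearest example. How many depends on taper shape and steroid potency, which the documents do not give, and on event counts, so the number affected is unknown.

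A reader might infer that dose-escalation decisions were distorted. The documents do not show this: the DLT definition in Section 3.2.3.3 does not refer to the Section 5.6.2 list, and no DLT or MTD effect is claimed.

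**What to change.** Add one item to the corticosteroid exceptions in Section 5.6.2: *systemic corticosteroids used to manage drug-related toxicity per Section 5.5.4, with resumption per Section 5.5.5 and subject to Sections 5.5.6 and 6.10.1*. This also gives the 6-week bullet in Section 6.10.1 its purpose back.

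SAP Section 1 says the study ended after Part A and that Part B and Phase 1b will not start, so the amendment would not change further enrolment. The useful step now is one sentence in the study report stating which rule was applied to subjects given systemic steroids for irAEs. The cost is one line of protocol text and that sentence; no new data, visits or subjects are needed.
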